Full Study Title

Hypoglossal Nerve Stimulation for Obstructive Sleep Apnea on Sympathetic and Vascular Function

Short Study Title CARDIOSA-12

Principal Investigator
[name], MSCR
Department of Otorhinolaryngology

Co-Investigator
[name]
Department of Otorhinolaryngology

Sponsors

American Heart Association
American Sleep Medicine Foundation

Protocol Version Number & Date Version 3.4 | 09/30/2021

- 1. Eligibility Criteria: All patients recruited into the study will have already been implanted with the Inspire® device. Additional inclusion criteria include:
 - As tolerating the therapeutic level during sleep can take time (weeks to months), all
 patients must be able to use the device at the therapeutic setting (> 20 hours per week for
 > 1 month) prior to enrollment based on compliance data.
 - The patients will be English-speaking and able to give written informed consent.

2. Exclusion Criteria

- Inspire® remote model 2500 or later is required. Patients with older remotes are not candidates due to limited adherence monitoring capabilities.
- Patients who have fallen asleep while driving resulting in accident or "near miss" accident within 1 year prior to HGNS implantation.
- Pregnant women will be excluded*
- Actively using positive airway pressure (PAP) therapy for treatment of OSA.
- Patients in whom the difference between sham and therapeutic voltages is within 0.1 V of 30% therapeutic voltage.
- * Women of child bearing potential must NOT be pregnant or plan on becoming pregnant. This study involves temporarily stopping treatment of obstructive sleep apnea, which may harm the fetus. If applicable, the patient will need to take a urine pregnancy test after enrollment (prior to washout #1), and again prior to washout #2.

3. Study Objectives

Primary Outcome Measure:

Change in mean 24-HOUR systolic ambulatory blood pressure values

Aim 1: Determine the impact of hypoglossal nerve stimulation on 24-hour systolic ambulatory blood pressure in this cohort of patients with moderate-severe obstructive sleep apnea

Hypothesis: The mean 24-hour systolic blood pressures will be improved at therapeutic levels of hypoglossal nerve stimulation and returned to pre-operative levels after 30-day sham period

Secondary Outcome Measures:

Change in mean 24-HOUR diastolic ambulatory blood pressure values

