- 2. HGNS Device Activation (1-month post-op): As part of usual care, patients return to the Otorhinolaryngology clinic 1 month post-operatively to undergo activation of the implanted device. At this visit, a functional threshold (in volts) is obtained based on tongue motion during device stimulation. The patient is provided detailed instructions on self-adjustment of stimulation levels using the remote control. For the next month, the patient will have steadily increased stimulation strength by 0.1V every 2-3 nights within the preset range until the upper limit is reached. The patient has the full support of the clinic nurse during this month to troubleshoot any issues.
- 3. Polysomnography (PSG) Titration (2-months post-op): Also as a component of usual care, two months after surgery, a level-I PSG (in accordance with 2014 American Academy of Sleep Medicine Manual for the Scoring of Sleep and Associated Events) is performed at the Sleep Center with standard parameters. Once asleep, the patient undergoes device titration of the HGNS starting at 0.2V below functional threshold. The voltage is sequentially increased by 0.1V until control of sleep-disordered breathing is achieved, providing "therapeutic amplitude" (treatment).

4B. Recruitment into the Cardiovascular Outcomes Study (variable months post-op): There are two different methods for recruitment:

1. An IRB-approved recruitment letter will be mailed to eligible HGNS patients, which will have contact information for the study team. If interested, the patient will reach out to the PI or the research study coordinator (RSC) who will mail or email (patient preference) a copy of the ICF for review. If contacted by the patient, RSC will obtain verbal consent and will coordinate an in-person visit with the patient at the Penn

- Otorhinolaryngology clinic. This visit will include informed consent and visit day one procedures. See 4C below.
- 2. At the patient's follow-up appointment, [name] will mention the study to the patient and provide a copy of the consent form. Informed consent discussion will be performed at this time. If the patient consents, study day 1 procedures will take place. See 4C below.
- Table 1: Age, gender, race, BMI, smoking status, Pre-op AHI, pre-op ODI, post-op AHI, post-op ODI, Months since implant, Hours of usage since activation, average weekly therapy use since last visit, diabetes status, HTN status, anti-HTN medications.

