- Eligibility Source documents: Initial consult note, pre-implant sleep study, pre-implant DISE report, HGNS titration report, HGNS efficacy sleep study report (if applicable), current medications list (reconciled), all Inspire® therapy reports leading up to enrollment.

4C. Study Timeline - Pages 5 to 10

- Enrollment (Study Day 1): HGNS therapy will be deactivated (set to 0.0 V) for one week. Sham threshold determination may be done during this visit, or during randomization visit (see below study week 2). RSC will schedule cardiovascular and sympathetic testing, if possible. The patient will also be instructed about neurobehavioral testing and will perform a practice administration of the DSST and PVT. Form 1 will be completed by RSC (remote #, current therapy status, non-dominant arm diameter, WatchPAT digit determination, medication reconciliation, sham threshold determination (volts), and active therapy setting (volts)). If needed, the patient will contact RSC after the appointment to provide the remote number. The patient will also be given an "on-study card" containing contact information for the research coordinator. The patient will be told to contact the coordinator if any health care providers intend to make changes to the patient's blood pressure medication. An enrollment questionnaire will be completed by the patient:
 - o Do you take any medications or substances to improve daytime alertness?
 - Do you take any medications or substances to improve sleep quality?
 - o How many hours do you sleep each night, on average?
 - ESS, ISI, FOSQ, Snoring VAS
- Washout Period 1 (Study Week 1): The patient will not use HGNS for 1 week
- Randomization Visit (Study Week 2 with [name] and RSC):
 - a. Patient will fill out "washout questionnaire":
 - Patient attestation statement about therapy non-use
 - Have you taken any substance to increase daytime alertness (e.g. caffeine)?
 - Have you taken any substance to improve sleep quality (e.g. alcohol)?
 - o Have you had any episodes of falling asleep while driving?

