- b. Sham Threshold Determination (Consent or Randomization Visit): Mouth open, nose breathe only, stimulation from 0.1V up by 0.1-0.2V at same electrode configuration as at last clinic visit, level at which bulk tongue motion detected without obvious protrusion. This process is repeated and the average value is used to determine "sham-HGNS". This threshold will be used to define "sub-therapeutic amplitude" (sham). The electrode configuration will remain consistent between the patient's therapeutic and sham thresholds.
- c. Randomization: The research coordinator will program the device at the specified amplitude level: either "sham-HGNS" as above, or "therapeutic HGNS," depending on which is assigned first (**see part d below**). The "therapeutic HGNS" setting will be the patient's incoming amplitude on enrollment day which will have been predetermined as part of routine clinical care prior to enrollment in the study. The patient control range will be deactivated for consistency, i.e. there will only be one allowable setting. The research coordinator will instruct the patient to use therapy the same night, and for every night until the next washout after cardiovascular test day (study week 6).
- d. Randomization technique: Both patients and investigators will remain blinded regarding patient intervention (sham or treatment HGNS). Only the research coordinator will remain unblinded; he will randomize the patients using a simple scheme (sealedenvelope.com) and will not take part in any assessments. Block design (block size = 10 with 10 units per block) for total of 100 potential subjects. Number 1 = Sham First, Number 2 = Treatment First.
- Blinding Adequacy Phone Call (Week 2, Day 2)

A blinded member of the study team, as delegated by the PI, will contact the patient and perform a verbal questionnaire:

- 1. Do you think you are on "low" or "regular" treatment, or do you not know?
- 2. Why you do think so?
 - a. Increased snoring per bed partner
 - b. Increased fatigue
 - c. Morning headache
 - d. Nighttime awakening
 - e. Other
- Weekly Check-In Phone Call (Week 3, Week 4, Week 5)

RSC weekly call with patient re: usage. Goal is to encourage use (>20h/week) RSC will document changes in blood pressure medication, if applicable. RSC will remind the patient to consistently take the blood pressure medication. Any questions, comments, concerns, or AEs will be documented at this time as well.

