 - 5. Exit Questionnaire
 - 6. The patient will resume usual care: the RSC will reprogram the patient's HGNS to the pre-study therapeutic amplitude and will reactivate the stimulation control range. The patient will be encouraged to contact the study team to address any problems or questions.

5. Variables:

Medical Chart: age, sex, race, smoking status, hypertension status, diabetes status, apnea-hypopnea index (AHI) from pre-operative sleep study, ODI from pre-operative study, pre-operative DISE report, history of PAP intolerance

Study Data (Clinical): body-mass index, current medications (recorded each study visit), therapy usage (hours/week)

Study Data (Experimental): mean systolic and diastolic blood pressures over 24 hours, mean systolic and diastolic blood pressures during sleep, WatchPAT ODI and AHI from both sham and active therapy tests, pre-ejection period (milliseconds), flow-mediated dilation, peripheral arterial stiffness (PWV in m/s, AIX, SEVR), Snoring Visual Analog Scale (VAS), Epworth Sleepiness Scale (ESS), Insomnia Severity Index (ISI), Functional Outcomes Sleep Questionnaire (FOSQ-10)

6. Analysis

The overall analysis plan is to examine changes in all cardiovascular endpoints over time (i.e., sham to treatment or treatment to sham) as well as internal correlation of these endpoints. Sex, a relevant biological variable, is a covariate in all analyses.

For **Aim 1**, we will perform a paired t-test to compare sham and active therapy 24-hour systolic ambulatory blood pressure values. Improvement in AHI will be calculated as the

difference between pre-operative and post-operative AHI. Multivariable linear regression models will be used to estimate associations between blood pressure reduction (outcome variable) and improvement in AHI (main effect variable) Final models will include age, sex, body-mass index, baseline systolic BP, baseline diastolic BP, antihypertensive medication use.

- H1: Therapeutic levels of HGNS will reduce mean 24-hour systolic pressures
- **H2:** Therapeutic levels of HGNS will further reduce mean sleep systolic and diastolic pressures

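### The sham–therapeutic voltage exclusion is written as a two-sided band: it excludes a gap of about 30% and admits smaller gaps. It should be a one-sided minimum.

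*Combined protocol and SAP*

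**What the plan says.** The only numeric condition on the distance between the two settings is in section 2, which excludes "Patients in whom the difference between sham and therapeutic voltages is within 0.1 V of 30% therapeutic voltage". The protocol gives no reason for the 30% or for the 0.1 V.

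The two voltages come from separate procedures:

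- **Therapeutic.** This is the amplitude the patient brings to enrollment. At the clinical titration (section 4A, item 3), "The voltage is sequentially increased by 0.1V until control of sleep-disordered breathing is achieved".
- **Sham.** Under Sham Threshold Determination (section 4C, item b), the coordinator applies "stimulation from 0.1V up by 0.1-0.2V at same electrode configuration as at last clinic visit" and looks for the "level at which bulk tongue motion detected without obvious protrusion". The process is repeated, and the average becomes the sub-therapeutic setting.

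On timing, the Enrollment entry in section 4C says: "Sham threshold determination may be done during this visit, or during randomization visit". Form 1, described in the same entry, records both voltages. Section 5 lists "WatchPAT ODI and AHI from both sham and active therapy tests" among the study data.

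**The concern.** A rule on voltage separation in a sham-controlled crossover would be expected to guard against a sham too close to active therapy. The primary hypothesis needs that: it expects blood pressure to go back to its pre-operative level on sham. The sentence as written does something else. Being within 0.1 V of a value describes a band around that value, so gaps below the band are as eligible as gaps above it.

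At stake is the contrast behind the Aim 1 paired comparison. A patient whose sham still delivers much of the therapy contributes a smaller sham–active difference in 24-hour systolic pressure. The plan has little slack for dilution: by its own figures, power with 60 patients is 0.80 at 4 mmHg (section 6) and 0.56 at 3 mmHg (section 10, Study Results).

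The sham voltage may not be known until the randomization visit, after the patient has spent a week off therapy. Staff need one unambiguous rule at that point.

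**Working it through.** **Inputs.** The rule is from section 2. Titration moves in 0.1 V steps (section 4A, item 3), and sham is sought in 0.1–0.2 V steps (section 4C, item b). The documents give no voltages, so T = 1.0, 2.0 and 3.0 V are assumptions chosen to show a range. The plan has no worked figure for this rule to reproduce.

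**Step 1: the rule as a formula.** Exclude if |(T − S) − 0.3T| ≤ 0.1 V, that is, if 0.3T − 0.1 ≤ T − S ≤ 0.3T + 0.1. In terms of sham, exclude if 0.7T − 0.1 ≤ S ≤ 0.7T + 0.1. The band is 0.2 V wide at every T.

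**Step 2: numbers, on a 0.1 V grid with S below T.**

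| Assumed T | Excluded gap | Gap as % of T | Sham excluded | Sham admitted with a smaller gap | Settings failing a plain 30% minimum (T − S < 0.3T) | Of these, admitted as written |
|---|---|---|---|---|---|---|
| 1.0 V | 0.2–0.4 V | 20–40% | 0.6–0.8 V | 0.9 V | 2 (0.8–0.9 V) | 1 |
| 2.0 V | 0.5–0.7 V | 25–35% | 1.3–1.5 V | 1.6–1.9 V | 5 (1.5–1.9 V) | 4 |
| 3.0 V | 0.8–1.0 V | 27–33% | 2.0–2.2 V | 2.3–2.9 V | 8 (2.2–2.9 V) | 7 |

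These are counts of possible settings, not of patients. The settings nearest T are the less likely ones, given how sham is defined. Because sham is an average of repeated determinations, values between grid points can also occur. The band in Step 1 does not depend on the grid.

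**Step 3: the rule is not monotone.** At T = 2.0 V, two 0.2 V steps down in sham give:

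- S = 1.6 V: gap 0.4 V (20%), admitted.
- S = 1.4 V: gap 0.6 V (30%), excluded.
- S = 1.2 V: gap 0.8 V (40%), admitted.

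**Step 4: does the unknown cut-off matter?** Take three candidate minima: 0.3T − 0.1, 0.3T and 0.3T + 0.1. At T = 2.0 V they are 0.5, 0.6 and 0.7 V. Each rejects every gap below 0.3T − 0.1, which is exactly the region below the band that the written rule admits. Any further gaps that the two higher cuts reject lie inside the band, where the written rule rejects them too. So the wrongly admitted settings are the same for all three: 0.9 V; 1.6–1.9 V; 2.3–2.9 V.

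The sentence could also be a slip for *0.1 V or 30%*. If either limb excludes, the cut is max(0.1, 0.3T), which equals 0.3T once T ≥ 0.1/0.3 = 0.33 V. If the smaller limb applies, the cut is 0.1 V. At T = 2.0 V only S = 1.9 V then fails, and the written rule admits that setting as well.

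**Step 5: does another section close the gap?** Sham is set by tongue motion short of clear protrusion, and therapy by control of breathing, so equal voltages are unlikely. Neither definition sets a distance in volts. The clinical functional threshold is also read from tongue motion, and titration starts 0.2 V below it (section 4A, items 2 and 3). A gap of a few tenths of a volt is therefore possible.

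**The case against.** The strongest reply is that this is loose wording that no one would apply literally. A coordinator would have to turn away clearly separated patients and accept nearly identical settings, although the sham is defined as sub-therapeutic. The fault may be one letter, *of* for *or*. No affected patient is shown. The comparison is within patient, so eligibility cannot unbalance the arms, and dilution works against finding an effect. WatchPAT results under both settings show the achieved contrast more directly than volts do. A strict 30% minimum could also cost recruitment in a trial that had enrolled 17 patients since January 2018 (section 9).

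Much of this stands. The intent is inferred, the cut-off is unsettled, nothing shows that staff used the literal band, and the recruitment cost cannot be estimated. It does not rescue the sentence. This is an operative eligibility rule, the only numeric safeguard on separation, and it gives the wrong answer for small gaps under every candidate cut-off. Dilution does not bias the trial towards a false positive, but it can hide a real effect. The WatchPAT data are collected, but the plan does not prespecify using them to check separation.

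**Conclusion.** The criterion is wrong as written. Read literally, it excludes only gaps within 0.1 V of 30% of T and admits every smaller one. Of the 0.1 V settings that fail a plain 30% minimum, it admits 1 of 2, 4 of 5 and 7 of 8 at assumed therapeutic voltages of 1.0, 2.0 and 3.0 V.

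Confidence is high about the wording and the arithmetic. It does not extend to the intended cut-off, to how staff applied the rule, or to any effect on results. The change should be made because the fault is definite and cheap to repair; harm has not been shown.

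**What to change.** 1. Replace the sentence with a one-sided minimum, for example: *exclude if therapeutic minus sham voltage is less than 30% of therapeutic voltage*.
2. Have the sponsor state the intended cut-off and what the 0.1 V was for, before anyone sees outcomes by arm. At T = 2.0 V the candidates are 0.5, 0.6 or 0.7 V, or 0.1 V under the smaller-limb reading.
3. From the Form 1 voltages, list enrolled patients who fail the clarified rule and keep them in the primary analysis. If none fail, say so.
4. Optionally, repeat the 24-hour systolic analysis without those patients, read alongside WatchPAT AHI and ODI under sham and active therapy.

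The cost is one sentence in an amendment and one listing. The optional analysis uses data already collected. Some future patients may change eligibility; how many cannot be said, because no voltages are given and recruitment status is unclear (section 9 planned completion in 2020, and this version is dated 09/30/2021). A cut-off fixed this late is credible only if it is set without sight of outcomes by arm.

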Hypothesis: The pulse wave velocity parameters will be improved at therapeutic levels of hypoglossal nerve stimulation and returned to pre-operative levels after 30-day sham period

Change in Digit Symbol Substitution Test (DSST) score

Aim 5: Determine the impact of hypoglossal nerve stimulation on digital symbol substitution test score in this cohort of patients with moderate-severe obstructive sleep apnea

Hypothesis: The digital symbol substitution test score will be improved at therapeutic levels of hypoglossal nerve stimulation compared to after 30-day sham period

Change in Psychomotor Vigilance Test (PVT) score

[figure not shown]
Aim 6: Determine the impact of hypoglossal nerve stimulation on psychomotor vigilance test score in this cohort of patients with moderate-severe obstructive sleep apnea

Hypothesis: The psychomotor vigilance test score will be improved at therapeutic levels of hypoglossal nerve stimulation compared to after 30-day sham period

4. Procedures and Data Collection

4A. *Pre-Study Procedures:* All patients in the cohort will have undergone implantation of HGNS for OSA at the University of Pennsylvania or Thomas Jefferson University as part of their ongoing care for their OSA. HGNS therapy is not experimental and is not under investigation per se for efficacy in this study. **Figure 3** shows the study flow. Patients will receive compensation for travel and time spent in the study (\$100 per visit, plus \$10 parking reimbursement for each cardiovascular measurement visit; total=up to \$520). Reimbursement for parking may also be available. Compensation will be pro-rated, and will be in the form of mailed checks and/or ClinCards.

Figure 3: Study Flow

Note: We will leave +/- 14 days at each step to accommodate for scheduling issues, etc.

- 1. HGNS Device Implantation: Under general anesthesia, the HGNS device is implanted via 3 incisions: right neck (stimulation lead), right upper chest (pulse generator) and right lower chest (respiratory sensor). The incisions are connected via a tunneling device, integrating the system components. The pulse generator, using technology from cardiac pacemakers, utilizes the signal from the pressure sensor for timing of stimulation to the tongue nerve. Patients are monitored in post-anesthesia recovery until stable for discharge. The device remains "off" for 1 month to allow for adequate healing.

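### The sham-voltage exclusion may be checked as late as the randomization visit, after a nominal week with the device off, although it could be checked on Day 1 (low priority)

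*Combined protocol and SAP*

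**What the plan says.** Section 2 (Exclusion Criteria) excludes "Patients in whom the difference between sham and therapeutic voltages is within 0.1 V of 30% therapeutic voltage".

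The sham voltage comes from the sham threshold determination, described in section 4C under the Randomization Visit, step b. Its timing is left open in two places. The Enrollment (Study Day 1) entry says "Sham threshold determination may be done during this visit, or during randomization visit", and the label of step b likewise names either the consent or the randomization visit.

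The same Day 1 entry states that "HGNS therapy will be deactivated (set to 0.0 V) for one week". The randomization visit follows in study week 2. Form 1, listed under Day 1, has fields for both the sham threshold and the active setting. Step c of the Randomization Visit defines the therapeutic setting as the amplitude the patient arrives with on enrollment day.

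The list at the end of section 4B that begins "Eligibility Source documents: Initial consult note, pre-implant sleep study, pre-implant DISE report, HGNS titration report" continues with the efficacy sleep study, the medication list and the device therapy reports. It does not include the sham threshold or Form 1.

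**The concern.** An eligibility rule should be settled before the patient bears a study burden, where that is possible. Here the burden is loss of therapy. The entry rule in section 1 says "patients must be able to use the device at the therapeutic setting (> 20 hours per week for" more than one month, so every entrant is an established user. Section 2 also excludes anyone "Actively using positive airway pressure (PAP) therapy for treatment of OSA", so at entry no PAP is in use alongside the stimulator. A patient who fails the voltage rule at the randomization visit has gone without usual therapy for a trial that will not randomize them. The risk-benefit argument in section 7 rests on knowledge gained, and such a patient contributes nothing to the sham-versus-active comparison.

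The protocol already applies this principle to another exclusion. Section 2 places the first pregnancy test before washout 1, because stopping treatment may cause harm. The voltage exclusion has no equivalent safeguard.

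**Working it through.** The plan gives no figure on this point to reproduce. The check is one of sequence, with a little arithmetic on exposure.

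**1. What the rule needs.** Write T for the therapeutic voltage and S for the sham voltage. Read literally, the exclusion applies when |(T − S) − 0.30 × T| ≤ 0.1 V. However the sentence is read, it involves S and cannot be evaluated without it.

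**2. When T is known.** On enrollment day, from routine care (section 4C, Randomization Visit, step c).

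**3. When S can be known.** On Day 1 at the earliest and at the randomization visit at the latest (section 4C, both places cited above).

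**4. Whether Day 1 is feasible.** Section 4B, recruitment route 1, describes an in-person clinic visit: "This visit will include informed consent and visit day one procedures". Route 2 performs the Day 1 procedures at a follow-up appointment. The device is set to 0.0 V on Day 1, and measurement that day is already a permitted option. The order of steps within Day 1 is not stated, so measuring before deactivation is possible but has to be written in.

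**5. Whether another text closes the gap.** Seven eligibility source documents are listed. All are existing clinical records or device reports, and none supplies S. I found no sentence requiring the voltage check before deactivation.

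**6. Exposure of a patient who fails late.**
- Nominal time at 0.0 V: 1 week = 7 days.
- Therapy forgone at the minimum use required for entry: more than 20 h/week × 1 week = more than 20 hours.
- Scheduling window: section 4A says "We will leave +/- 14 days at each step to accommodate for scheduling issues, etc". If this applies to the step, the upper end is 7 + 14 = 21 days. Figure 3, to which the note belongs, is not shown, so this cannot be confirmed, and 7 days is the figure to use.
- With the check done before deactivation: 0 days.

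**7. Effect on the comparison.** Step b (sham determination) is listed before step c (randomization). A patient excluded at step b is never randomized. Sample size, power and alpha are unchanged.

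**8. Frequency.** The documents give neither the proportion of patients whose measurement is deferred nor the proportion who meet the exclusion. The number affected is the product of these two and the number enrolled, so it cannot be calculated and may be zero.

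**The case against.** The best defense is that Day 1 already looks like the default. Form 1 is a Day 1 form with a field for the sham threshold, and deferral is only permitted, not directed. That may well describe practice, and it lowers the priority. It does not remove the option, which is written twice.

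Second, the burden is modest beside what participants consent to: two one-week washouts and a four-week sham period. A patient who fails late has one washout and none of the rest, and the coordinator could restore the usual amplitude at that same visit. This is fair, and it limits the size of the point. It does not make the week necessary.

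Third, making Day 1 measurement mandatory has a price. Under route 2, Day 1 follows consent at a routine appointment, and the determination is repeated and averaged, so time or staff may be short. This objection stands and is counted as a cost of the fix.

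Fourth, a Day 1 value might be thought stale by week 2. The protocol already accepts older values. At the week 7 crossover the device is programmed from Form 1, so treatment-first patients receive a sham voltage measured about 7 − 2 = 5 to 7 − 1 = 6 weeks earlier.

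Three stronger readings are tempting but not supported:
- A reader might infer that late exclusion biases the trial. It does not, because it precedes randomization.
- A reader might infer that patients lose a treatment known to work. Entry is based on hours of use, and section 10 (Study Results, item a) acknowledges that some patients will not reach therapeutic success on polysomnography. The supportable statement is that they lose their usual therapy.
- A reader might try to bound the frequency from section 9, which reports 17 recruited and 16 completed. That difference covers loss for any reason, may omit screen failures and may predate the criterion, so it bounds nothing here.

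**Conclusion.** The gap is real and minor. As written, a patient can spend a nominal 7 days off usual therapy before a check that could have been made on Day 1. The issue is avoidable patient burden and risk, not validity.

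The conclusion rests on two assumptions: that the deferral option means what it says, and that measuring before deactivation is practicable at an ordinary Day 1 visit. The documents permit Day 1 measurement but do not show that every such visit has room for it. I would label this a cheap improvement of low priority.

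**What to change.** In section 4C, under Enrollment (Study Day 1), require the sham threshold determination and the voltage exclusion check, both recorded on Form 1, before the device is set to 0.0 V. State that a patient who meets the exclusion stays on the usual setting. In step b of the Randomization Visit, change the label so that the determination belongs to the consent/enrollment visit. If it cannot be done that day, deactivation waits until it has been. A repeat determination at the randomization visit need not be prohibited.

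The cost is protocol wording, a slightly longer Day 1 visit, and less scheduling flexibility for patients whose measurement would otherwise have been deferred; some may start washout later. No new procedure is added.
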